5.3 Safety Analysis Set (SAF)

The Safety Analysis Set (SAF) consists of all randomized subjects who received a vaccination in this study with either ASP3772, PCV13, or PPSV23.

The SAF will be used for most summaries of demographic and baseline characteristics and all safety and tolerability related variables.

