7.2 Analysis Sets

The Safety Analysis Set (SAF) will consist of all subjects who receive an immunization in this study with either ASP3772, PCV13, or PPSV23. The Full Analysis Set (FAS) will consist of all subjects who receive an immunization in this study with either ASP3772, PCV13 or PPSV23 and have at least 1 postimmunization measurement.

For each ASP3772, PCV13 or PPSV23 immunization group, the number and percentage of subjects in each analysis set will be given for all randomized (ASP3772 or PCV13) or enrolled (PPSV23) subjects.

O2 Dec 2019 Astellas Page 69 of 111

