5.1 Full Analysis Set (FAS)

The Full Analysis Set (FAS) will consist of all subjects who receive an immunization in this study with either ASP3772, PCV13 or PPSV23 and have at least 1 post immunization measurement.

The FAS will be used for summaries and primary analyses of immunogenicity data.

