7.2 Study Population

7.2.1 Disposition of Subjects

The following subject data will be presented:

- Disposition: number of subjects with informed consent, discontinued before randomization, randomized and immunized;
- Analysis sets: number and percentage of subjects in the safety analysis set (randomized and received an immunization, full analysis set (randomized, immunized, and at least 1 post baseline endpoint evaluation) and per protocol analysis set (if needed) (subjects who did not receive antibiotics within 7 days of their Day 30 blood draw; subjects who have their Day 30 blood draw between Day 30 and Day 44; subjects who have not received immunosuppressants; subjects who do not have newly diagnosed immunologic abnormalities within the first 2 weeks after receiving the immunization);
- Treatment discontinuation: number and percentage of randomized subjects who completed and who discontinued treatment, by primary reason for treatment discontinuation (adverse event, death, lost to follow-up, protocol deviation, withdrawal by subject, other);

- Discontinuation up to 30 days: number and percentage of randomized subjects who completed and who discontinued the 30-day investigational period, by primary reason for discontinuation (adverse event, death, lost to follow-up, protocol deviation, withdrawal by subject, other);
- Discontinuation after Day 30 up to Day 180: Number and percentage of randomized subjects who completed and who discontinued during the follow-up period (post Day 30 through Day 180), by primary reason for discontinuing during the follow-up period (adverse event, death, lost to follow-up, protocol deviation, withdrawal by subject, other); subjects in Group 3 will not be followed beyond Day 30.
- Per protocol exclusions: Number and percentage of subjects excluded from PPS by reason for exclusion defined in Section 5.2, by treatment group.

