7.5 Analysis of Safety

All analysis of safety will be presented by treatment group (ASP3772 (1 µg, 2 µg, 5 µg) or PCV13) and stage for SAF. All adult subjects who receive PCV13 will be combined into a single group and all elderly subjects who receive PCV13 will be combined into a single group. Safety data for subjects given PPSV23 will not be compared with any other treatment group since these subjects were not a randomized treatment group.

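### The SAP requires randomization for the safety set (and, in 7.2.1, the full analysis set), which contradicts its own inclusion of the nonrandomized PPSV23 group

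*SAP*

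**What the plan says.** **Safety analysis set (SAF).** Protocol 7.2: "The Safety Analysis Set (SAF) will consist of all subjects who receive an immunization in this study with either ASP3772, PCV13, or PPSV23". SAP 5.3 adds a condition: the set "consists of all randomized subjects who received a vaccination in this study with either ASP3772, PCV13, or PPSV23". The list of disposition displays in SAP 7.2.1 repeats it: "number and percentage of subjects in the safety analysis set (randomized and received an immunization".

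**Full analysis set (FAS).** SAP 5.1, the formal definition, has no such condition: the set "will consist of all subjects who receive an immunization in this study with either ASP3772, PCV13 or PPSV23 and have at least 1 post immunization" (that is, one result recorded after vaccination). SAP 7.2.1 describes it differently: "full analysis set (randomized, immunized, and at least 1 post baseline endpoint evaluation".

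**Status of the PPSV23 group.** Protocol 3.3 and 5.1.1 call Group 3 nonrandomized. SAP 3.3 describes its subjects only as enrolled. SAP 7.5 rules out a safety comparison with other groups "since these subjects were not a randomized treatment group". For the analysis-set counts, Protocol 7.2 gives the base as "all randomized (ASP3772 or PCV13) or enrolled (PPSV23) subjects".

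**What is to be produced.** SAP 5.3 assigns the safety and tolerability variables, and most demographic and baseline summaries, to the SAF. SAP 7.1 promises separate summaries for the PPSV23 subjects, Protocol 7.3 promises a demographic summary for them, and SAP 7.4.1 lists their antibody summaries.

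**The concern.** Programmers build population flags from the definitions in the SAP. A flag that requires both randomization and vaccination cannot be true for any Group 3 subject enrolled as planned. The PPSV23 safety and baseline summaries would then have no subjects. If the FAS flag were taken from 7.2.1 rather than 5.1, the Group 3 immunogenicity summaries would be empty too.

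There is a further practical reason to get the safety set right. SAP 3.2 removes PPSV23 recipients without prior PCV13 from the immunogenicity summaries. The safety set is where those vaccinated people should still be counted, and the literal rule would lose them there as well.

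The readable entries in SAP 8 do not explain why the SAP's safety set differs from the protocol's. Some entries in that list are blacked out, so little weight rests on this.

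**Working it through.** **Step 1. Reproduce the planned numbers** (cohort tables in Protocol 2.2.1 and SAP 3.2).

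- Stage 1: 3 × (30 + 10) = 120, as stated.
- Stage 2 Group 2: 3 × (99 + 33) = 396, as stated.
- Stage 2 Group 3: 99, as stated.
- Stage 2 total: 396 + 99 = 495, which matches Protocol 7.1.
- Study total: 120 + 396 + 99 = 615.

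**Step 2. Apply each rule to a vaccinated Group 3 subject who has a measurement after vaccination.** This subject is vaccinated but not randomized.

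| Rule | Randomization required? | Group 3 subject |
|---|---|---|
| SAF, Protocol 7.2 | no | in |
| SAF, SAP 5.3 | yes | out |
| SAF, SAP 7.2.1 | yes | out |
| FAS, Protocol 7.2 | no | in |
| FAS, SAP 5.1 | no | in |
| FAS, SAP 7.2.1 | yes | out |

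**Step 3. Planned SAF size by arm**, assuming that every planned subject is vaccinated.

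| Arm | Protocol 7.2 | SAP 5.3 read literally |
|---|---|---|
| Stage 1 ASP3772 (3 × 30) | 90 | 90 |
| Stage 1 PCV13 (3 × 10) | 30 | 30 |
| Stage 2 ASP3772 (3 × 99) | 297 | 297 |
| Stage 2 PCV13 (3 × 33) | 99 | 99 |
| Stage 2 PPSV23 | 99 | 0 |
| Total | 615 | 516 |

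The loss is confined to one row. It is 99/495 = 20.0% of Stage 2 and 99/615 = 16.1% of the study. These percentages give scale only: the SAP reports safety by treatment group and stage, with PPSV23 separate, and describes no safety analysis pooled over all 615.

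**Step 4. Check the disposition items.** The discontinuation items in SAP 7.2.1 count randomized subjects, yet the item for the period after Day 30 adds a remark that Group 3 is not followed that long. The remark has a purpose only if Group 3 belongs in these displays, so the stated denominator does not fit their content.

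**The case against.** The best defence is that nobody would apply the sentence literally.

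- SAP 5.3 names PPSV23 in the very sentence at issue. On the literal reading that term would cover no planned subject.
- The documents use randomization loosely for this group. The title of Table 3, the Group 3 schedule, dates prior PCV13 relative to randomization, and the Group 3 remark in SAP 7.2.1 points the same way.
- SAP 7.1, in its paragraph on SAF-based summaries, promises PPSV23 output.
- SAP 1 provides for a review of data and tables before hard lock, and empty PPSV23 tables would show up there.

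All of this stands as evidence of intent. A reader might infer that the SAP deliberately drops a study arm; the documents do not support that. It does not make the definition right, however. Protocol 7.2 drew the distinction between randomized and enrolled subjects explicitly, and the SAP lost it in two sections.

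Three other inferences are tempting and should be resisted.

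- *The primary safety result is compromised.* The Stage 2 primary objective compares ASP3772 with PCV13 (Protocol 2.1, SAP 3.1), and Step 3 shows those planned denominators unchanged. Group 3 has only immunogenicity endpoints (Protocol 2.3, SAP 6.1.2), and its safety data are compared with no other group.
- *The PPSV23 benchmark for immunogenicity is lost.* Those summaries use the FAS, and the formal definition in SAP 5.1 keeps Group 3. Only the parenthesis in 7.2.1 conflicts with it.
- *Vaccinated Group 1 or 2 subjects without a randomization record would vanish from safety.* The literal rule would do this to such a subject, but the documents describe no such case. Kits are assigned through the IRT (Protocol 4.5), so the point does not rest on this hypothetical.

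**Conclusion.** The concern holds as an inconsistency in the population rules. The SAF definition in SAP 5.3, repeated in 7.2.1, conflicts with its own mention of PPSV23, with Protocol 7.2 and with SAP 7.1. Read literally, it leaves the Group 3 safety and baseline summaries with 0 of about 99 planned subjects. The FAS conflict is narrower and lies only in 7.2.1.

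No planned ASP3772 or PCV13 denominator, estimate or test changes, and neither does any sample size or error rate. The conclusion assumes that Group 3 is enrolled as described, without randomization, and treats 99 as an approximate planned number. Inclusion of PPSV23 subjects is plainly intended, so the risk is one of programming and traceability. It should be corrected because the rule governs the population that carries all the safety output, and the correction costs almost nothing.

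**What to change.** 1. SAP 5.3: delete *randomized*, so that the SAF is everyone vaccinated in the study with one of the three vaccines, as in Protocol 7.2.
2. SAP 7.2.1: describe the SAF as in Protocol 7.2 and the FAS as in SAP 5.1, or simply refer to those definitions. For the FAS this also replaces the post-baseline endpoint wording with the post-immunization wording of 5.1, so that one definition applies throughout.
3. SAP 7.2.1: base the analysis-set and disposition percentages on "all randomized (ASP3772 or PCV13) or enrolled (PPSV23) subjects". Protocol 7.2 already sets this base for the analysis sets; using it for the disposition items as well gives Group 3 a denominator.
4. Carry the same rules into the population-flag specification, and record the change in the SAP revision section.

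The cost is a few words in the SAP and the flag specification. No new data are needed and no comparison changes.

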5.4 Pharmacokinetic Analysis Sets (PKAS)

Not applicable for this protocol.

5.5 Pharmacodynamic Analysis Set (PDAS)

Not applicable for this protocol.

6 ANALYSIS VARIABLES

In this Phase 1/2 study, the primary endpoints are safety-related. All immunogenicity endpoints are secondary endpoints.

6.1 Efficacy Endpoints

6.1.1 Serotypes

The 13 serotypes contained in PCV13 are: 1, 3, 4, 5, 6A, 6B, 7F, 9V, 14, 18C, 19A, 19F, 23F. The 23 serotypes contained in PPSV23 are: 1, 2, 3, 4, 5, 6B, 7F, 8, 9N, 9V, 10A, 11A, 12F, 14, 15B, 17F, 18C, 19A, 19F, 20A, 22F, 23F, and 33F. ASP3772 is a 24-valent MAPS vaccine and contains the following serotypes: 1, 2, 3, 4, 5, 6A, 6B, 7F, 8, 9N, 9V, 10A, 11A, 12F, 14, 15B, 17F, 18C, 19A, 19F, 20B, 22F, 23F and 33F. The tables below illustrate the commonalities.

	Serotypes Common to PCV13												
PCV13	1	3	4	5	6A	6B	7F	9V	14	18C	19A	19F	23F
PPSV23	1	3	4	5		6B	7F	9V	14	18C	19A	19F	23F
ASP3772	1	3	4	5	6A	6B	7F	9V	14	18C	19A	19F	23F

	Serotypes Not Contained in PCV13											
PCV13												
PPSV23	2	8	9N	10A	11A	12F	15B	17F	20A	22F	33F	
ASP3772	2	8	9N	10A	11A	12F	15B	17F	20B	22F	33F	

Serotype 20A is unique to PPSV23 and serotype 20B is unique to ASP3772. In this study there is only an assay for 20B. Serotype 20A has shown some cross reactivity with 20B.

6.1.2 Secondary Endpoint(s)

Stage 1, Group 1:

Surrogate markers used to assess the immunological response on day 30 for the 13 serotypes common to ASP3772 and PCV13 are:

- Functional OPA activity for each serotype characterized by an OPA titer⁻¹ response expressed as the reciprocal of the serum dilution that causes a 50% reduction in the colony-forming units
- Pneumococcal serotype-specific anticapsular polysaccharide PS IgG for each serotype.

Summaries of immune response 30 days after immunization in adults 18 to 64 years of age will be provided for each serotype by treatment group (ASP3772 (1 µg, 2 µg, 5 µg) or PCV13) and stage. All adult subjects treated with PCV13 will be combined into a single group. To assess similarity between the 3 cohorts of PCV13 subjects, summaries will be provided by cohort for the PS IgG levels and the OPA titers.

Endpoints used to assess the immunological response on day 30 for the 11 serotypes unique to ASP3772 (2, 8, 9N, 10A, 11A, 12F, 15B, 17F, 20B, 22F, 33F) are:

- Geometric mean fold rise (GMFR) in anticapsular PS IgG at 30 days relative to pre-immunization
- Proportion of subjects with a ≥ 4 -fold increase in anticapsular PS IgG
- Functional OPA activity for each serotype characterized by an OPA titer⁻¹ response

Stage 2; Group 2:

Endpoints used to assess the immunological response on day 30 are:

- Functional OPA activity for each serotype characterized by an OPA titer⁻¹ response
- Pneumococcal serotype-specific anticapsular PS IgG for each serotype for the 13 serotypes contained in PCV13
- For each of the 11 serotypes unique to ASP3772, the GMFR in anticapsular PS IgG at 30 days relative to pre-immunization
- For each of the 11 serotypes unique to ASP3772, the proportion of subjects with a ≥ 4 -fold increase relative to baseline in anticapsular PS IgG for ASP3772 and PCV13-treated subjects

For Stage 2, Group 2 summaries will be provided by treatment group (ASP3772 (1 μ g, 2 μ g, 5 μ g) or PCV13) for all subjects age 65-85, for subjects 65-74 and for those 75-85. Subjects treated with PCV13 in cohorts 4, 5 and 6 will be combined into a single dose group and summarized by age (65-85, 65-74 and 75-85). To assess similarity between the 3 cohorts of PCV13 subjects, summaries will be provided by cohort for the PS IgG levels and the OPA titers.

In addition, for ASP3772, the following endpoints will be assessed.

- Dose response in the OPA titer⁻¹ for ASP3772
- Dose response in the PS IgG antibodies for ASP3772

[figure not shown]
Stage 2; Group 3:

For the 11 serotypes contained in PPSV23 and not in PCV13, immunological response will be evaluated by the following endpoints at 30 days after administration of PPSV23:

[figure not shown]
- Functional OPA activity characterized by an OPA titer⁻¹ response
- Pneumococcal serotype-specific anticapsular PS IgG

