Enroll	To register or enter a subject into a clinical study. Note: Once a subject has received the study drug or placebo, the clinical study protocol applies to the subject.			
Intervention The drug, device, therapy or process under investigation in a clinic is believed to have an effect on outcomes of interest in a study (e.g related quality of life, efficacy, safety and pharmacoeconomics).				
Investigational period	Period of time where major interests of protocol objectives are observed, and where the test drug or comparative drug (sometimes without randomization) is usually given to a subject, and continues until the last assessment after completing administration of the test drug or comparative drug.			
Post investigational period	Period of time after the last assessment of the protocol. Follow-up observations for sustained adverse events and/or survival are done in this period.			
Randomization	The process of assigning study subjects to treatment or control groups using an element of chance to determine assignments in order to reduce bias.			
Screening	A process of active consideration of potential subjects for enrollment in a study.			
Screen failure	Potential subject who did not meet 1 or more criteria required for participation in a study.			
Screening period	Period of time before entering the investigational period, usually from the time when a subject signs the consent until just before the test drug or comparative drug (sometimes without randomization) is given to a subject.			
Study period	Period of time from the first site initiation date to the last site completing the study.			
Variable	Any entity that varies; any attribute, phenomenon or event that can have different qualitative or quantitative values.			

IV. SYNOPSIS

Date and Version No of Protocol Synopsis:	02 Dec 2019, Version 2.1
Sponsor:	Protocol Number:
Astellas Pharma Global Development Inc. (APGD)	3772-CL-1001
Name of Study Drug:	Phase of Development:
ASP3772	Phase 1/2

Title of Study:

A Phase 1/2, Randomized, Single Ascending Dose Study in Adults (Stage 1) and Randomized, Single Ascending Dose-Finding Study (Stage 2) in Elderly Subjects with ASP3772, a Pneumococcal Vaccine

Planned Study Period:

Stage 1: 1Q2019 – 2Q2019 Stage 2: 3Q2019 – 3Q2020

Study Objective(s):

Stage 1:

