After all subjects complete dosing in Cohort 1 (low dose, 1 μ g of ASP3772 or PCV13), safety (including reactogenicity) and tolerability through 7 days postimmunization will be assessed by the DEC. Assessments of safety and tolerability by the DEC will occur prior to initiating the next dose group, Cohort 2 (2 μ g of ASP3772 or PCV13) and then Cohort 3 (5 μ g of ASP3772 or PCV13), based on safety and tolerability data through 7 days postimmunization.

Safety and tolerability assessments will continue through 30 days postimmunization. Safety assessments for serious adverse events (SAEs) and medically attended adverse events (MAAEs) including potential immune-mediated medical conditions (PIMMCs) and NOCDs will continue through day 180 postimmunization. Data will be collected in an observer-blinded manner (vaccine recipients and any site staff who is responsible for evaluation of any study endpoint will be unaware of which vaccine the subject received).

Serum samples to measure IgG and opsonophagocytic activity (OPA) will be collected prior to the first study immunization on day 1 and on day 30 postimmunization.

Stage 2 Group 2:

Stage 2 of the study is a dose-finding (sequentially higher doses), active-controlled, observer-blinded study with 3:1 randomization (ASP3772:PCV13) in elderly subjects 65 to 85 years of age.

After screening, PCV13 naïve subjects will be randomized within each cohort to receive ASP3772 or PCV13. Subjects randomized to ASP3772 will receive a single dose of ASP3772 administered as a 0.5 mL intramuscular injection into the deltoid muscle of the right or left arm on day 1, at 1 of 3 dose levels: 1, 2 or 5 µg of ASP3772 for Cohorts 4, 5 and 6, respectively. The subjects randomized to PCV13 will receive a single injection of the standard dose of PCV13.

Approximately 396 subjects will be enrolled in Stage 2 of the study; 132 subjects per cohort (ASP3772 n = 99 and PCV13 n = 33).

Stage 2 will commence after the DEC has evaluated safety (including reactogenicity) data through 30 days from all cohorts in Stage 1. Dose escalation to Cohort 5 (intermediate dose, 2 µg) in Stage 2 will commence once the DEC has evaluated Stage 2 Cohort 4 (1 µg) safety (including reactogenicity) and tolerability through 7 days postimmunization. Dose escalation into Cohort 6 (high dose, 5 µg) in Stage 2 will commence once the DEC has evaluated Stage 2 Cohort 5. Randomization for Stage 2 subjects will be stratified by age (65 to 74 years

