3.2 Study Design

This is a combined phase 1, first-in-human (FIH), dose-escalation (Stage 1) and phase 2, dose-finding (Stage 2) study to evaluate the safety, tolerability and immunogenicity of ASP3772 in adult subjects and in elderly subjects.

The objectives of this study are to evaluate safety, tolerability including reactogenicity and immunogenicity in adult subjects 18 to 64 years of age in Stage 1 and in elderly subjects

65 to 85 years of age in Stage 2, who are naïve to licensed or investigational pneumococcal vaccine.

The study population will consist of 3 different groups: **Group 1** - Stage 1 subjects randomized within 3 sequential cohorts to ASP3772 or PCV13; **Group 2** - Stage 2 PCV13 naïve subjects randomized within 3 sequential cohorts to ASP3772 or PCV13; and **Group 3** - Stage 2 subjects previously vaccinated with PCV13 will receive PPSV23.

To minimize the risk to subjects, a sentinel group of subjects (n = 2; 1 ASP3772:1 PCV13) will be vaccinated in each cohort prior to initiating enrollment of the full cohort. Safety data through day 7 from sentinel subjects will be evaluated by the Dose Escalation Committee (DEC) prior to enrolling the remainder of the cohort. Safety data through day 7 from all subjects within a dose cohort will be evaluated by the DEC prior to escalating to the next dose cohort within the adult and within elderly subjects. Based on the safety data through 30 days after immunization from the first 3 cohorts, the DEC will determine if Stage 2 can

commence, and if sentinel dosing is required for Stage 2. A DEC charter will detail the roles, responsibilities and procedures for decision-making.

Stage 1, Group 1: Stage 1 of the phase 1/2 design is a randomized, active-controlled, observer-blinded, dose- escalation study of the safety, tolerability and immunogenicity of the ASP3772 pneumococcal vaccine in adult subjects (18 to 64 years of age) compared with PCV13 with a 3:1 randomization (ASP3772:PCV13). The syringe used to administer PCV13 is distinct. The vaccine administrator will differ from the person evaluating reactogenicity to remove reporting bias for any reactogenicity events. Additionally, treatment assignment will be unknown to the full study team.

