Subjects will be enrolled sequentially into 1 of 3 cohorts designated by escalating ASP3772 dose levels. A single dose of ASP3772 will be administered as a 0.5 mL intramuscular (IM) injection on day 1 at 1 of 3 dose levels: 1, 2 or 5 µg of ASP3772. The subjects randomized to PCV13 will receive a single injection of the standard dose of PCV13 on day 1.

Approximately 120 subjects will be enrolled in Stage 1 of the study, 40 subjects per cohort (ASP3772 n = 30 and PCV13 n = 10).

After all subjects complete dosing in Cohort 1 (low dose, 1 µg of ASP3772 or PCV13), safety (including reactogenicity) and tolerability through 7 days postimmunization will be assessed by the DEC in a blinded manner. Assessments of safety and tolerability by the DEC will occur prior to initiating the next dose group, Cohort 2 (2 µg of ASP3772 or PCV13) and then Cohort 3 (5 µg of ASP3772 or PCV13), based on safety and tolerability data through 7 days postimmunization. The DEC Charter will provide details for revealing the treatment assignment for individual subjects to DEC members, if necessary.

Safety and tolerability assessments will continue through 30 days postimmunization. Safety assessments for serious adverse events (SAEs) and medically attended adverse events (MAAEs) including potential immune-mediated medical conditions (PIMMCs) and new-onset chronic disease (NOCD) will continue through day 180 postimmunization. Data will be collected in an observer-blinded manner (vaccine recipients and those responsible for evaluation of any study endpoint will be unaware of which vaccine the subject received).

Serum samples to measure pneumococcal serotype-specific anticapsular polysaccharide (PS) immunoglobulin G (IgG) and functional opsonophagocytic activity (OPA) will be collected prior to the first study vaccination on day 1 and on day 30 postimmunization.

The design schematic for Stage 1 is shown in the table below. There will be a total of approximately 120 evaluable adults 18 to 64 years of age.

Number of Subjects per Cohort by Immunization

Cohort	Stage 1 (Group 1)			
	ASP3772	Number of Subjects	Comparator	Number of Subjects
1	1 µg	30	PCV13	10
2	2 µg	30		10
3	5 µg	30		10

PCV13: Prevnar 13

Stage 2, Group 2:

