Stage 2 of the study is a dose-finding (sequentially higher doses), active-controlled, observer-blinded study with a 3:1 randomization (ASP3772:PCV13) in elderly subjects 65 to 85 years of age (Group 2). For Stage 2, Group 2 subjects the vaccine administrator will differ from the person evaluating reactogenicity to remove reporting bias for these events. Treatment assignment will also be unknown to the blinded study team.

After screening, PCV13 naïve subjects will be randomized within each cohort to receive ASP3772 or PCV13. Subjects randomized to ASP3772 will receive a single dose of ASP3772 administered as a 0.5 mL intramuscular (IM) injection on day 1, at 1 of 3 dose levels: 1, 2 or 5 µg of ASP3772 for Cohorts 4, 5 and 6, respectively. The subjects randomized to PCV13 will receive a single injection of the standard dose of PCV13.

Stage 2 will commence after the DEC has evaluated safety (including reactogenicity) data through 30 days from all cohorts in Stage 1. Dose escalation to Cohort 5 (intermediate dose, 2 µg) in Stage 2 will commence once the DEC has evaluated Stage 2 Cohort 4 (1 µg) safety (including reactogenicity) and tolerability through 7 days postimmunization. Dose escalation into Cohort 6 (high dose, 5 µg) in Stage 2 will commence once the DEC has evaluated Stage 2 Cohort 5. The DEC will review the data for each cohort in Stage 2, Group 2 in a blinded manner. The DEC Charter will provide details for revealing the treatment assignment for individual subjects to DEC members, if necessary. Randomization for Stage 2 subjects will be stratified by age (65 to 74 years of age and 75 to 85 years of age) to ensure there is a balanced number of subjects within each age cohort immunized with either ASP3772 or PCV13.

Safety and tolerability assessments including adverse events (AEs) will continue through 30 days postimmunization. Safety assessments for SAEs and MAAEs including PIMMCs and NOCDs will continue through day 180 postimmunization. Data will be collected in an observer-blinded manner (vaccine recipients and the site staff who are responsible for evaluation of any study endpoint will be unaware of which vaccine the subject received).

Serum samples to measure IgG and OPA will be collected prior to study vaccination on day 1 and postimmunization on day 30. The primary immunogenicity evaluation for dose finding is 30 days following the initial immunization.

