7.4 Analysis of Immunogenicity

7.4.1 Analysis of Immunogenicity Endpoints

Assessment of immunological response following ASP3772 administration relative to PCV13 is a secondary objective for this study.

Stage 1, Group 1 and Stage 2, Group 2:

The objective in Stage 1, Group 1 and Stage 2, Group 2 is to determine if ASP3772 stimulates an immunogenic response to the 13 pneumococcal serotypes that are also contained in PCV13 and to determine if ASP3772 stimulates an immunogenic response to an additional 11 serotypes contained in ASP3772. The following summaries will be given by treatment group (ASP3772: 1, 2, 5 μ g vs. PCV13) and stage for all serotypes.

OPA Titer

- GMT, GSD and 95% CI
- The ratio of the OPA GMT (each ASP3772 dose level/PCV13), the GSD and 95% CI for the ratio
- The GMFR relative to baseline, GSD and 95% CI
- The proportion of subjects with a $>$ 4-fold increase in OPA titer¹

IgG Concentration

- The GMC, GSD and 95% CI
- The ratio of the IgG GMC (each ASP3772 dose level/PCV13), the GSD and 95% CI
- The GMFR relative to baseline, GSD and 95% CI
- The proportion of subjects with a \geq 4-fold increase in anticapsular PS IgG

Values below the LLOQ will be set to $\frac{1}{2}$ LLOQ for calculation of geometric means and set to LLOQ for calculation of fold changes.

Summaries for Stage 2 subjects will be given for 65-85, 65-74 and 75-85-year olds.

An analysis of covariance (ANCOVA) model with age (65 to 74 years, 75 to 85 years) as the covariate and treatment (ASP3772 1, 2, 5 μ g) as the factor of interest will be conducted on the natural logarithm (log) of pneumococcal OPA titers and on the natural log of the IgG concentrations for each serotype to examine dose response. Provided the treatment effect is

significant, paired comparisons between the 5 μ g vs 1 μ g, followed by 5 μ g vs 2 μ g, followed by 2 μ g vs 1 μ g will be conducted. There are no adjustments to control for the Family-Wise Error Rate (FWER) for 3 comparisons for each of the 24 serotypes. A Cochran-Armitage trend test will be used to test for trend.

CCI

Stage 2; Group 3:

The objective for Stage 2, Group 3 is to obtain estimates of the immune response following PPSV23 for the 11 serotypes contained in PPSV23 and not in PCV13. Immunological response 30 days after administration of PPSV23 will be summarized as follows:

- The GMT, GSD and 95% CI for the OPA titers
- The GMC, GSD and 95% CI for serotype-specific IgG levels.

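### Each dose is randomised against PCV13 only within its own sequential cohort, yet the readable SAP text estimates every ratio against pooled PCV13 and compares doses across cohorts, without a concurrent-control sensitivity analysis

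*SAP*

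**What the plan says.** **Design.** SAP 3.2 states that in Stage 2 Group 2 "PCV13 naïve subjects will be randomized within each cohort to receive ASP3772 or PCV13". Each cohort holds a single ASP3772 dose, and the cohorts are sequential: Cohort 6 "in Stage 2 will commence once the DEC has evaluated Stage 2 Cohort 5". Protocol 2.2.1 plans "132 subjects per cohort (ASP3772 n = 99 and PCV13 n = 33"), and the synopsis gives Stage 2 a planned period of "3Q2019 – 3Q2020". Stage 1 has the same structure, with "40 subjects per cohort (ASP3772 n = 30 and PCV13 n = 10").

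**Ratios to PCV13.** SAP 6.1.2 says that "Subjects treated with PCV13 in cohorts 4, 5 and 6 will be combined into a single dose group", and SAP 7.1 applies the same pooling by age group in both stages. SAP 7.4.1 forms each GMT and GMC ratio as dose over PCV13. Appendix A tests it with a two-sample t-test on logs, with no cohort term.

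**Dose response.** SAP 7.4.1 specifies "An analysis of covariance (ANCOVA) model with age (65 to 74 years, 75 to 85 years) as the covariate" and dose (1, 2, 5 µg) as the factor. If dose is significant overall, 5 v 1, 5 v 2 and 2 v 1 µg are compared. PCV13 is not in this model. The ANCOVA in Protocol 7.4 includes PCV13 as a level but, like the SAP's, has no cohort term.

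**Existing check.** SAP 6.1.2 also plans summaries of PCV13 IgG and OPA by cohort, to see whether the three PCV13 groups are alike. It attaches no criterion or follow-up analysis.

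**Use.** SAP section 4 says that Stage 2 responses will determine the phase 3 dose and sample size.

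**The concern.** Randomisation protects the comparison of a dose with the PCV13 subjects of its own cohort. It does not protect a comparison with PCV13 subjects from other cohorts, nor a comparison of one dose with another. If the population, the sites or the response to vaccination change between cohorts, that change enters the day 30 ratios and is indistinguishable from dose in the ASP3772-only ANCOVA.

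Some change is plausible. The protocol amendment of 02 December 2019 falls after the planned start of Stage 2. It added sites to help Group 2 recruitment, dropped the hepatitis B core antibody exclusion and lengthened Stage 2 screening, and it records that sentinels are no longer needed from Cohort 5 onward. The documents do not give cohort dates or say whether any of this altered responses.

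At stake is the reading of the dose response that feeds the phase 3 choice.

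**Working it through.** **1. The plan's own figures.** Group 2: 3 × (99 + 33) = 396. Stage 1: 3 × (30 + 10) = 120. Both match the documents. The sample size rests on 95% CI widths for a single arm's OPA GMT, but neither the GSDs nor the widths are printed, so the widths cannot be reproduced. In units of the log SD the half-width t(0.975, n−1)/√n is 0.373, 0.198 and 0.161 for n = 30, 100 and 150. None of these concerns a ratio or a dose contrast.

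**2. Non-concurrent controls.** Stage 2: 99 − 33 = 66 of 99. Stage 1: 30 − 10 = 20 of 30. Two thirds in each case.

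**3. What the models can separate.** A model with an intercept, three dose indicators and two cohort indicators has rank 6 of 6 on the planned Stage 2 layout when PCV13 is included. With ASP3772 arms only, the same columns have rank 3: dose and cohort are the same variable.

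**4. Bias under drift (assumption).** Suppose there is no true difference between vaccines or doses, and responses in both arms are multiplied by d at each cohort step. On the log scale the cohort shifts are 0, ln d and 2 ln d, so pooled PCV13 sits at ln d.

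| Comparison | Log bias | Factor at d = 1.10 |
|---|---|---|
| 1 µg / pooled PCV13 | −ln d | 0.91 |
| 2 µg / pooled PCV13 | 0 | 1.00 |
| 5 µg / pooled PCV13 | +ln d | 1.10 |
| 5 µg / 1 µg | 2 ln d | 1.21 |

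These factors do not depend on the GSD.

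**5. Rejection rates (GSD assumed 5 to 3).** SE = ln(GSD) × √(2/99) = 0.229 at GSD 5 and 0.156 at GSD 3. Two-sided rejection = P(|Z + bias/SE| > 1.96), with ln 1.10 = 0.0953.

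- 1 or 5 µg / PCV13: standardised bias 0.0953/0.229 = 0.42 to 0.0953/0.156 = 0.61, giving 7% to 9% instead of 5%.
- 5 v 1 µg, ungated: standardised bias 0.83 to 1.22, giving 13% to 23%.
- 5 v 1 µg after a significant overall test, as the SAP requires (simulated without the age term): about 8% to 15%, against about 2.5% with no drift.

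**6. How much the by-cohort PCV13 summaries could show.** With 33 per cohort, the difference between two PCV13 cohorts detectable with 80% power is exp{(1.96 + 0.8416) × √(2/33) × ln GSD}: 2.1-fold at GSD 3. Even a 1.2-fold drift per step (1.44-fold from Cohort 4 to Cohort 6) would be detected with power of only 27% at GSD 3.

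**7. Price of concurrent control (in log SDs).**

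- Dose/PCV13: pooled √(1/99 + 1/99) = 0.142; concurrent √(1/99 + 1/33) = 0.201; ratio 1.41. Stage 1 gives 0.258 and 0.365, again 1.41.
- Dose v dose: planned √(2/99) = 0.142; relative to concurrent PCV13 √{2(1/99 + 1/33)} = 0.284; ratio 2.0.
- The 95% interval factor for an anchored dose contrast is exp(1.96 × 0.284 × ln GSD): 1.84 at GSD 3 and 2.45 at GSD 5.

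**The case against.** **The information is already planned.** Each dose is one cohort, and PCV13 will be summarised by cohort, so a reader could build the concurrent ratios by hand. This stands in part: it would be wrong to say that the plan never looks at cohort differences. But those tables give levels. No concurrent ratio, interval or anchored dose contrast is prespecified.

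**Redaction.** SAP 7.4.3 on dose response and part of 7.4.1 are blacked out. This stands: a cohort adjustment there cannot be excluded, and the point covers only the readable text.

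**Not every shift becomes a vaccine effect.** A reader might infer that any change over time contaminates every result. The SAP also plans GMFR for IgG and OPA, and a multiplicative assay shift common to a subject's day 1 and day 30 samples cancels there. Changes in vaccine response do not.

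**The drift is assumed, and 5 v 1 µg is the worst contrast.** Correct. The documents support no particular drift or GSD; the ratios are affected less, and the 2 µg ratio not at all under linear drift. Immunogenicity is secondary, and the SAP openly declines family-wise control.

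**The remedy is weak.** Anchored dose contrasts have interval factors of 1.84 to 2.45, against an illustrative bias of 1.21. For the 11 serotypes not in PCV13, the comparator lacks the antigen and cannot track drift in vaccine response. Both limits stand and belong in the SAP.

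**Protocol v SAP.** It is tempting to say that the SAP removed a safeguard by leaving PCV13 out of the ANCOVA. It did not: the protocol's model has no cohort term, so it gave no within-cohort anchoring either. That mismatch is a separate matter.

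**Conclusion.** The point holds for the readable text. The GMT and GMC ratios use controls of whom two thirds are non-concurrent, and the SAP dose-response ANCOVA cannot distinguish dose from cohort. Pooling is prespecified and is not an error; the gap is that the comparison actually randomised is never reported as a ratio, interval or contrast.

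The size depends on assumptions. At 10% drift per cohort, the bias is at most 1.10-fold for a ratio (or its reciprocal, 0.91) and 1.21-fold for 5 v 1 µg. The ungated 13–23% should not be read as the plan's error rate, since the SAP's gate lowers it. Nor do the documents show that drift occurred, or that phase 3 will rest on the dose contrasts alone; they refer to Stage 2 responses generally.

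**What to change.** Keep the pooled analysis as main and add to SAP 7.4.1 a prespecified sensitivity analysis:

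- (a) each dose/PCV13 ratio, with its 95% CI, against the PCV13 subjects of the same cohort;
- (b) for the 13 shared serotypes, dose contrasts relative to concurrent PCV13, from a model with cohort, arm (ASP3772 or PCV13), cohort-by-arm and age stratum, PCV13 included.

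State that for the 11 serotypes not in PCV13 this bridge addresses only assay or baseline drift, so dose contrasts there remain non-randomised comparisons across cohorts. If the redacted text already contains such an analysis, a cross-reference is enough.

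The cost is extra tables from data already being collected, and wider intervals: SE × 1.41 for dose/PCV13 and × 2.0 for dose contrasts. The SAP should say that this analysis can reveal large cohort effects but that agreement with the pooled result does not exclude modest drift.
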